1. INTRODUCTION

Nitric oxide (NO) is a recognised biological mediator in humans and has been implicated in the pathophysiology of lung diseases including asthma and eosinophilic airway inflammation. NO is produced in the human lung and is present in exhaled breath. The measurement of fractional exhaled nitrous oxide (FeNO) has now been standardized for clinical use. Numerous studies have already provided evidence regarding the clinical applications of FeNO measurements. The role of FeNO measurements in *asthma* has been well established and practice guidelines regarding its clinical applications have been published (Dweik *et al.*, 2011). However, the exact role of FeNO measurements and its clinical implications remain unclear in the context of Chronic Obstructive Pulmonary Disease (COPD). This exploratory study aims to further clarify the utility of FeNO in the setting of acute exacerbations of COPD (AECOPD).

^{1.} St John of God Midland Private and Public Hospital. [name].

2. BACKGROUND

Fraction of Expired Nitric Oxide measurement

NO gas is produced in the epithelial cells of the bronchial wall in response to interleukin-4 and -13, which are produced locally by the TH2 cells, mast cells, and eosinophils. FeNO indicates the presence of pro-inflammatory cytokines due to eosinophilic airway inflammation. Advances in technology and standardization have made FeNO measurement simple and rapid permitting its use as a point-of-care biomarker in the assessment of inflammatory airways diseases.

Expired Nitric Oxide in Asthma

FeNO has been used as a marker for TH2-mediated airway inflammation in asthma and has been shown to correlate with airway inflammation and to be reduced by corticosteroid therapy. FeNO measurement are currently recommended in asthma to support the diagnosis of eosinophilic airway inflammation; determine the likelihood of steroid responsiveness; monitor airway inflammation and guide changes in anti-inflammatory therapy (Dweik *et al.*, 2011). In adults with asthma, a FeNO above 50 parts per billion (ppb) identifies patients who are likely to respond to steroids, while a FeNO below 25ppb identifies those who are not (Smith *et al.*, 2005).

Eosinophils and Expired Nitric Oxide in COPD

In patients with COPD increased, yet variable, eosinophil numbers have been detected in sputum, BAL samples and airway biopsies. However, compared with asthma, less is known about the role of eosinophils in the pathogenesis of COPD. This is despite the finding that sizable proportion of patients with COPD have eosinophilic inflammation (Saha e Brightling, 2006). Interest in the phenotyping of airway diseases has led to the recognition of an asthma-COPD overlap population in which some patients diagnosed with asthma also have features of COPD and vice versa. Patients with asthma-COPD overlap syndrome (ACOS) account for 15%—20% of COPD patients with greater disease morbidity compared with those with COPD alone. Although the underlying pathobiology of ACOS is largely unclear, recent genomic studies have demonstrated a potential role of TH2 inflammation and eosinophil activation.

A recent review (Bafadhel *et al.*, 2017) on the clinical significance of peripheral eosinophil counts and COPD management suggest that circulating eosinophils during stable COPD may help predict risk of mortality and risk of exacerbations. Additionally, in patients at the onset of an acute exacerbation blood eosinophilia may be used to identify those with worse outcomes and predict risk of further exacerbations (Vedel-Krogh *et al.*, 2016), hospital readmission (Couillard *et al.*, 2017), length of hospital stay, response to corticosteroids (Pizzichini *et al.*, 1998; Brightling *et al.*, 2000) and mortality (Hospers *et al.*, 2000). Despite the above findings, results from trials evaluating the use of eosinophils in guiding the treatment of COPD, both during stable disease and exacerbations, are still pending.

FeNO indicates the presence of pro-inflammatory cytokines due to eosinophilic airway inflammation and its measurement offers an attractive potential biomarker that may be useful for risk stratification and management of COPD patients. However, little is known about the FeNO levels in patients with COPD and ACOS and the exact role of FeNO measurements in these patients is still being defined.

To date, studies assessing FeNO in COPD patients have identified the following:

1. FeNO measurements in COPD patients

- The median FeNO concentration in stable COPD patients is 15-20ppb (Beg et al., 2009; Rouhos et al., 2011; Donohue et al., 2014) and higher during acute exacerbation of COPD 17-25 ppb , (Zhu et al. Int J Clin Exp Med 2016; 9: 10565-10571). On average, these levels are lower than those seen with asthma.
- Repeatability of FeNO in moderate to very severe stable COPD subjects (n= 20) has been shown to be adequate (Rouhos *et al.*, 2011).

2. FeNO in stable COPD patients

- FeNO is significantly elevated compared with normal controls. The elevations however appear to be less than in asthmatic subjects (Beg *et al.*, 2009).
- FeNO predicts a clinically significant increase in FEV1 in response to short term treatment with corticosteroids. In these patients, a high FeNO > 50ppb only had a modest positive predictive value (67%) for steroid responsiveness, however a low FeNO <25ppb had a high negative predictive value (87%) (Kunisaki *et al.*, 2008; Dummer *et al.*, 2009).
- Greater FeNO variability has been reported in patients with stable COPD who subsequently develop exacerbations (de Laurentis et al Pulm Pharmacol Ther 2008; 21:689-693).

The clinical implication of these findings is that FeNO levels in stable COPD patients may aid deciding in whom to initiate or escalate inhaled corticosteroid therapy.

3. FeNO during acute exacerbations COPD

- FeNO has been shown to be elevated in COPD exacerbations (Bhowmik et al., 2005).
 However this elevation is significantly lower than in patients with acute exacerbations of bronchial asthma (Zhu et al Int. J. Clin. Exp Med. 2016).
- o In patients admitted with COPD exacerbations FeNO on admission was a strong predictor of a clinically significant increase in FEV1 following treatment. FeNO below the optimum cut-point of 27ppb predicted the absence of any significant improvement in spirometry with a negative predictive value of 85% (Antus *et al.*, 2010).

The clinical implication of these findings is that FeNO levels may predict the response to treatment during acute exacerbations of COPD.

4. Risk of recurrent exacerbations

 Antus et al.'s (Acta Physiologica Hungarica 2013; 100: 469-77) follow-up retrospective study of COPD patientsadmitted with an acute exacerbation found a correlation between low FeNO levels (<27ppb) and increased number of exacerbations per patient year and hospitalization days due to further exacerbations over a 3 year period.

This finding should be interpreted with caution as it is opposite to what was seen with peripheral eosinophil counts being correlated to risk of readmission. (Couillard et al., 2017)

5. FeNO mechanism in COPD

- Exhaled nitric oxide correlates with eosinophilic airway inflammation in COPD. FeNO
 was higher in stable COPD patients with sputum eosinophilia (29ppb) than those
 without (18ppb) (Chou et al., 2014).
- However, it remains unclear what an elevated FeNO in AECOPD is due to and if it is acting as a surrogate marker of eosinophilic airway inflammation or if an alternative aspect of airway pathophysiology is at play.

Clinical implications of this study

COPD is one of the leading causes of disability and mortality worldwide. Patients with COPD may suffer recurrent exacerbations. COPD exacerbations are complex events usually associated with increased airway inflammation, increased mucous production and marked gas trapping. These changes contribute to increased dyspnea that is the key symptom of an exacerbation. Other symptoms include increased sputum purulence and volume, together with increased cough and wheeze. COPD exacerbation result in a worsening of symptoms and reduction in lung function that may not be recovered in a proportion of patients. Furthermore, exacerbations are associated with an impaired quality of life, reduced survival, and a high healthcare expenditure. The latter mainly results from admission to hospital which is frequently a consequence of an exacerbation. Prevention of exacerbations is therefore an important goal in the management of stable COPD, although knowledge about which factors relate to COPD exacerbations or hospitals admissions for exacerbations is currently very limited.

Patients who suffer a COPD exacerbation are at risk of further hospital admissions, with up to 15% and 35% requiring readmission at 30 and 90 days respectively. Risk for hospital readmission in COPD are increased age, increased severity of airflow obstruction (GOLD stage 4), reduced physical activity and associated comorbidities. One of the predictors of hospital readmission for AECOPD is a previous admission in the preceding 12 months with risk of readmission increasing with every additional admission event. Identifying potentially reversible causes of readmission and targeting specific interventions to a subgroup of these at risk patients may aid in modifying their long-term and short-term outcomes.

FeNO measurement is a simple and rapid point-of-care test that can be performed easily in the in-patient as well as the out-patient setting. This exploratory study aims to further clarify the role of FeNO in the setting of AECOPD and assess its association with risk of readmission. Identifying patients at greater risk of readmission may potentially help target interventions in this population.

3. AIM(S) OF STUDY

Exploratory study to evaluate FeNO levels in patients during and following recovery from an admission with an acute exacerbation of COPD.

4. OBJECTIVES

The objectives of the study are:

- 1. To determine if FeNO levels measured in the first 24 hours of admission to hospital for an AECOPD correlates to readmission risk at 12 months (and time to readmission).
- 2. To determine if FeNO levels measured in the first 6 weeks after discharge from hospital for an AECOPD correlates to readmission risk at 12 months (and time to readmission).
- 3. To determine if FeNO levels measured in the first 24 hours of admission to hospital for an AECOPD predict FEV1 improvement at 6 week follow-up.
- 4. To determine if FeNO levels measured in the first 24 hours of admission to hospital for an AECOPD predict CAT improvement at 6 week follow-up.
- 5. To describe the relationship between FeNO levels measured in the first 24 hours of admission to hospital for an AECOPD and blood eosinophil count.
- 6. To describe changes in FeNO levels between the first 24 hours of admission to hospital for AECOPD and at 6 week follow-up.

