5. HYPOTHESIS

5b. Primary Hypothesis

There is evidence that the presence of a raised blood eosinophil count in patients with an AECOPD may predict the risk of hospital readmission(Couillard *et al.*, 2017). FeNO correlates with eosinophilic airway inflammation in COPD (assessed by measuring sputum eosinophilia). (Chou *et al.*, 2014)

We hypothesize that patients with higher FeNO levels during and/or at 6 weeks recovery from an admission with an AECOPD are at higher risk of hospital readmission in the subsequent 12 months.

5b. Secondary Hypotheses

FeNO correlates with eosinophilic airway inflammation in COPD, a *potentially* reversible and steroid responsive component of airflow obstruction in patients with an acute exacerbation.

We hypothesize that patients with higher FeNO levels during and/or at 6 weeks recovery from an admission with an AEOPD are more likely to respond to steroid (inhaled and/or systemic) therapy with improved FEV1 measurements.

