10. STUDY OUTCOMES

10a. Primary Outcome

 Hospital re-admission for COPD within 12 months defined as admitted to hospital, excluding emergency department presentation only, with discharge diagnosis on the discharge summary being "Exacerbation of COPD".

10b. Secondary Outcome(s)

- Time to hospital re-admission for COPD (up to 12 months)
- Repeat exacerbation of COPD within 12 months, defined as an acute worsening of respiratory symptoms that results in increased dose of systemic corticosteroids and /or antibiotics. This outcome will be self reported.
- Change in FeNO levels between Day 1 of admission and on follow-up visit at 6 weeks.
- Change in FEV1, FVC, FEV1/FVC between Day 1 of admission and on follow-up visit at 6 weeks.
- Change in CAT score between Day 1 of admission and on follow-up visit at 6 weeks.

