11. STUDY PROCEDURES

11a. Recruitment of participants

Screening will take place before consent. The respiratory physician involved in the study will approach potential study participants within 24 hours of admission for a primary diagnosis of AECOPD. If they fulfill inclusion criteria and have no exclusion criteria they will be invited to participate in this study. They will be provided with written information about the research and given the opportunity to ask questions regarding participation. The participant will have up to 2 hours to decide if they wish to participate. Once informed consent is given they will be considered participants. We aim to recruit 80 participants. From a small audit (10 patients) performed in 2017 we expect that 60% of patients asked to participate will be able perform FeNO and spirometry testing essential for recruitment. Those who cannot complete either FeNO or spirometry will be excluded from final analysis as they cannot contribute to the primary outcome. However, as this is a potential source of bias we will collect all other data and follow-up outcomes from these patients also. We expect 12 months will be necessary to recruit 80 patients who can perform both FeNO and Spirometry on admission.

11b. Randomisation

This is a prospective observational cohort study. No randomization is required. No case matching is required.

11c. Study procedure

We will approach potential study participants within 24 hours of admission for a primary diagnosis of AECOPD. If they fulfill inclusion criteria and have no exclusion criteria they will be asked to participate in this study. Once informed consent is given they will be considered participants. Patient questionnaire, FeNO and spirometry testing will be performed at Day 1 (recruitment day) and at 6-week follow-up appointment. A further questionnaire via phone contact will be performed at 3, 6, 9 & 12 months. If the participant cannot be contacted by phone, the study will contact the nominated next-of-kin and general practitioner. The patient's general practitioner will be informed of study participation. This study does not involve any treatment intervention. All additional tests, except FeNO measurement, are considered part of usual care. Additional tests include spirometry and blood testing (FBC, IgE and RAST) and will be used to identify individuals who may have Asthma COPD Overlap Syndrome (ACOS). These tests can be "added on" to bloods taken on admission. The study does not

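### Objective 2 lets readmissions that occur before the 6-week FeNO count as outcomes of it, because no clock starts at that visit

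*Protocol*

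**What the plan says.** Section 4 sets two parallel objectives on readmission. Objective 1 uses the FeNO from the first 24 hours of admission. Objective 2 asks whether "FeNO levels measured in the first 6 weeks after discharge from hospital for an AECOPD correlates to readmission risk at 12 months". Both also name time to readmission.

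Section 11c fixes when FeNO is taken: "FeNO and spirometry testing will be performed at Day 1 (recruitment day) and at 6-week follow-up appointment". Follow-up after that is by telephone: "A further questionnaire via phone contact will be performed at 3, 6, 9 & 12 months".

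Section 10a has one primary outcome, which serves both FeNO measurements: "Hospital re-admission for COPD within 12 months defined as admitted to hospital, excluding emergency department presentation only". The time-to-event version in section 10b also runs up to 12 months and has no separate origin for the second FeNO. Section 12b enters FeNO level into a logistic model, and into a Cox or logistic model for the time outcomes, without mentioning a landmark, delayed entry or a time-dependent covariate.

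The primary hypothesis (section 5) covers FeNO during the admission and/or at 6 weeks, and says that patients with higher levels "are at higher risk of hospital readmission in the subsequent 12 months".

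**The concern.** A predictor should be known before the outcome it is meant to predict. Objective 2 uses a value obtained at about week 6 and an outcome window that is not restarted there. A patient readmitted in week 3 who attends in week 6 is then an event attributed to a FeNO that did not yet exist. In the Cox model, the weeks before the visit are counted as time at risk for a covariate not yet measured.

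There is a second problem. The early readmission and its treatment may themselves change the week-6 FeNO, so part of any association could run from outcome to predictor. The 6-week FeNO is one of the two predictors in the primary hypothesis, so its odds ratio and hazard ratio need a clear prognostic meaning.

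**Working it through.** **Order of events.** FeNO for objective 2: the 6-week appointment (section 11c). Outcome: COPD readmission within 12 months, one definition for both FeNO time points (section 10a). Start of the outcome clock: not stated. Rule for readmissions before the visit: none in sections 4, 10, 11 or 12b. Taken together, these provisions leave pre-visit readmissions inside the outcome.

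**Inputs for the size.** The protocol gives no 6-week readmission rate, so there is no figure of its own to reproduce. The Background describes patients at risk of further admissions, "with up to 15% and 35% requiring readmission at 30 and 90 days respectively". Section 11a gives the planned number: "We aim to recruit 80 participants". I take the visit to be on day 42 (an assumption; section 11 does not say whether it is counted from admission or discharge).

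**Share readmitted by day 42, at the stated upper limits.**

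- Linear interpolation: 0.15 + (0.35 − 0.15) × (42 − 30)/(90 − 30) = 0.15 + 0.20 × 0.20 = 19.0%
- Piecewise exponential between days 30 and 90: 1 − 0.85 × (0.65/0.85)^(12/60) = 19.4%
- Constant hazard from the 90-day rate: 1 − 0.65^(42/90) = 18.2%
- Constant hazard from the 30-day rate: 1 − 0.85^(42/30) = 20.3%
- Weibull through both points (shape 0.887): 19.7%

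The method matters little: 18.2% to 20.3%. For 80 patients the linear figure is 0.19 × 80 = 15.2.

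**Sensitivity.** The rates are upper limits, so 19% is a ceiling. Scaling both (an assumption):

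| Fraction of stated rates | Share by day 42 | Of 80 patients |
|---|---|---|
| 100% | 19.0% | 15.2 |
| 75% | 14.3% | 11.4 |
| 50% | 9.5% | 7.6 |

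Objective 2 speaks of the first 6 weeks, whereas section 11c specifies the 6-week appointment. If the measurement fell on day 35, the five methods would give 15.4% to 17.3% at the upper limits.

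**Length of the window after the visit.** If the 12-month contact is counted from recruitment or discharge, 52 − 6 = 46 weeks remain, and 46/52 × 12 ≈ 10.6, so about 10.5 months.

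**Can FeNO be changed by the early event?** Section 12b says that systemic steroids can affect FeNO. The Background says corticosteroids reduce it, but in the part on asthma. It also reports higher medians in COPD exacerbation (17–25 ppb) than in stable COPD (15–20 ppb). One mechanism would lower the week-6 value and the other would raise it.

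**The case against.** The strongest reply is that the primary hypothesis says "are at higher risk of hospital readmission in the subsequent 12 months", which is naturally read as after the measurement. On that reading no outcome precedes its predictor. The reading is fair, but it does not resolve the matter. The hypothesis covers both FeNO measurements with one phrase, sections 4 and 10 do not repeat the restriction, and contacts end at 12 months. If those contacts are counted from recruitment or discharge, a full 12 months after the visit is not observed.

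A statistical analysis plan could set a landmark. That is possible, but the objective and the outcome window are fixed in the protocol, and a landmark would change what they say.

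Section 12b also plans an analysis by systemic corticosteroid dose before FeNO measurement, and section 11c collects steroid prescriptions during and after the hospital stay. This addresses one route by which FeNO may be altered. It leaves pre-visit readmissions in the outcome, and for the 6-week FeNO the dose may itself result from such a readmission.

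Three points about size and direction stand against a stronger reading:

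- A reader might infer that 19% is the expected share. The source rates are upper limits and are not stated to be restricted to COPD, whereas the outcome requires a discharge diagnosis of COPD exacerbation. Patients who do not attend the visit supply no 6-week FeNO at all.
- A reader might infer that 38% to 48% of all events precede the predictor (0.19/0.50 and 0.19/0.40). That needs a 12-month rate, which the protocol does not give. At an assumed 60% to 70% the share would be 32% to 27%.
- A reader might infer that the bias runs against the hypothesis and would produce a spurious inverse association. The steroid effect stated as a reduction concerns asthma, and FeNO is reported as higher during COPD exacerbations. Any simulated odds ratio or error rate would rest on FeNO shifts that the documents do not supply.

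**Conclusion.** The ordering fault holds and does not depend on the percentage: as written, objective 2 can count readmissions that occurred before its predictor was measured, in both the logistic and the Cox model. Up to about 19% of patients (about 15 of 80) could be affected, or roughly 10 to 14% if true rates are 50 to 75% of the stated limits. These figures rest on interpolation, a day-42 visit and rates not stated to be COPD-specific. The association may be distorted in either direction. The study is exploratory and the fault can be corrected before analysis.

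**What to change.** In sections 4, 10 and 12b, define objective 2 as a landmark analysis:

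- Set time zero at the date of the 6-week visit, and count only COPD readmissions after it, up to the 12-month contact, in both the logistic and the Cox model.
- State the origin of the 12-month contact and that the window for objective 2 is about 10.5 months. Align the wording of the hypothesis with it.
- Report the number of patients readmitted, and the number who died, before the visit.
- Keep patients who were readmitted earlier but attend the visit, with pre-visit readmission as a covariate, and exclude them in a sensitivity analysis.

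This takes about one paragraph and no new data. The cost is fewer events and a slightly shorter window for objective 2. Objective 1 needs no change on this account.

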5. HYPOTHESIS

5b. Primary Hypothesis

There is evidence that the presence of a raised blood eosinophil count in patients with an AECOPD may predict the risk of hospital readmission(Couillard *et al.*, 2017). FeNO correlates with eosinophilic airway inflammation in COPD (assessed by measuring sputum eosinophilia). (Chou *et al.*, 2014)

We hypothesize that patients with higher FeNO levels during and/or at 6 weeks recovery from an admission with an AECOPD are at higher risk of hospital readmission in the subsequent 12 months.

5b. Secondary Hypotheses

FeNO correlates with eosinophilic airway inflammation in COPD, a *potentially* reversible and steroid responsive component of airflow obstruction in patients with an acute exacerbation.

We hypothesize that patients with higher FeNO levels during and/or at 6 weeks recovery from an admission with an AEOPD are more likely to respond to steroid (inhaled and/or systemic) therapy with improved FEV1 measurements.

